6.25 Loss/Removal of Implant and/or Implant Magnet

Any loss or removal of the BI300 Implant and/or BIM400 Implant Magnet should be recorded on the Adverse Events page in the Case Report Form (CRF), together with the reason for the loss or removal.

6.26 Device deficiency reporting

The definition of a device deficiency is an inadequacy of a medical device with respect to its identity, quality, durability, reliability, safety or performance.

A device deficiency should be reported to the Sponsor. A device deficiency that could have lead to a Serious Adverse Event (SAE) should be reported immediately (see next section).

6.27 Adverse Event (AE) and Serious Adverse Event (SAE)

6.27.1 Definitions

Term	Definition
Adverse Event (AE)	Any untoward medical occurrence, unintended disease or injury, or untoward clinical signs (including abnormal laboratory findings) in subjects, users or other persons, whether or not related to the medical device used in the investigation*. This definition includes events related to the procedures involved.
Adverse Device Effect (ADE)	Adverse event related to the use of medical device used in the investigation*. 
 • This definition includes adverse events resulting from insufficient or inadequate instructions for use, deployment, implantation, installation, or operation, or any malfunction of the investigational medical device. • This definition includes any event resulting from use error or from intentional misuse of the investigational medical device.
Serious Adverse Event (SAE)	A SAE** is an adverse event that: 
 • results in death • is life-threatening • requires inpatient hospitalisation or prolongation of existing hospitalisation • results in persistent or significant disability/incapacity • is a congenital anomaly/birth defect • has led to a important medical event that may have jeopardised the subject or may have required an intervention to prevent one of the above characteristics/ consequences. These can include complaints that might have led to a medical occurrence if 
 ○ suitable action had not been taken or ○ intervention had not been made or ○ if circumstances had been less fortunate. 
NOTE: Planned hospitalization for a pre-existing condition, or a procedure required by the CIP, without serious deterioration in health, is not considered a serious adverse event.

Serious Adverse Device Effect (SADE)	Adverse device effect that has resulted in any of the consequences characteristic of a serious Adverse Event
Unanticipated Serious	Serious adverse device effect which by its nature, incidence, severity or

Adverse Device Effect (USADE)	outcome has not been identified in the current version of the risk analysis report
Device deficiency	Inadequacy of a medical device with respect to its identity, quality, durability, reliability, safety or performance NOTE Device deficiencies include malfunctions, use errors, and inadequate labelling.

* The definition is broader than the definition in ISO14155:2011 since it includes all clinical investigations regardless if the medical device(s) is an investigational device or not.

** The definition is broader than the definition in ISO14155:2011 since it includes important medical event as a reportable event (see 6.26.3).

6.27.2 Handling and reporting of AEs

Subjects will be carefully monitored during the investigation for possible AEs and appropriate treatment of the subject will be initiated.

Any AE observed will be fully investigated by the investigator and documented in the case report form (CRF) including assessment of severity (mild, moderate or severe) and relationship to the medical device.

6.27.3 Reporting of SAEs and device deficiency that could have lead to a SAE

An investigator should report within 24 hours, after being aware of the event, an SAE or a device deficiency that could have lead to a SAE. The report should be sent as an e-mail attachment to Cochlear Bone Anchored Solutions AB. Instructions and contact information is available on the SAE form.

6.27.4 Reporting to ethics committees/investigational review boards

SAEs/SADEs/USADEs and device deficiencies that could have led to a SAE should be reported to ethics committees/investigational review boards in accordance with local requirements.

6.28 Concomitant medication and treatments

All medications and treatments given, whether or not to treat AEs/ADEs, must be recorded in the appropriate section of the CRF.

6.29 Extra visit(s)

Extra visit(s) may be a scheduled visit in order to change wound dressing or to follow-up any complications. These visits will be recorded on extra pages in the CRF. The following information will be recorded:

- Date
- Reason for extra visit
- Procedures and/or treatment used
- Staff that conducted the visit (surgeon, surgical nurse or audiologist)

7 Risk and benefits of the devices and the clinical investigation

7.1 Anticipated clinical benefits

The Baha Attract System is regulatory approved/cleared for the intended use in the present investigation. With the Baha Attract System, the subjects will be able to benefit from the Baha sound processor without an abutment penetrating the skin, thus providing cosmetic advantages compared to a traditional Baha. In addition, with the Baha Attract System, there is reduced need for daily cleaning to maintain a healthy implant site compared to a percutaneous Baha, and risk of adverse tissue reactions related to the percutaneous passage are eliminated.

It is expected that the audiological performance of the Baha Attract System will be similar to, or somewhat better than, Baha on a Softband. The performance in the high frequency range are likely to be slightly lower for subjects with the Baha Attract System compared to the percutaneous solution, due to transcutaneous attenuation of the vibrations through the skin.

Participation in the investigation requires slightly more frequent follow-up visits for the subject than what is normally required, and the duration of the visits will be slightly longer than normal. The more frequent visits will provide the subject the opportunity to more frequently interact with the treating physician. Subjects will receive compensation for travelling expenses made for extra visits to the clinic.

7.2 Residual risks associated with the device and procedures

Risks associated with the transcutaneous coupling that cannot be completely eliminated include magnetic retention difficulties, pressure-related skin complications and pain/discomfort. The system has been designed to minimise these risks. For example:

- The SP Magnet has been designed with a Soft pad on the soft tissue facing surface to evenly distribute the pressure, thus minimising the occurrence of peak pressure areas.
- To minimise the risk of pressure-related complications, the transcutaneous coupling has been designed such that the average pressure over the skin should not exceed 0.4 N/cm² (capillary blood pressure) and peak pressures should not exceed 0.6 N/cm² (diastolic blood pressure).
- The surgeons are instructed to carefully thin the soft tissue flap during surgery if the skin thickness exceeds 6 mm, to ensure good magnetic retention.
- Subjects with a soft tissue flap thickness of less than 3 mm are not included in the investigation.
- Sound processor loading shall be performed at 4 weeks post surgery. However, if the wound is not sufficiently healed, loading should be delayed.
- The investigators and the subjects will be instructed to carefully select an appropriate SP Magnet by balancing the magnet retention to avoid any skin problems.

The surgical procedure associated with the Baha Attract System is described in the Surgery Guide for the Baha Attract System. The guide has been developed by the Sponsor together with a group of experienced Baha surgeons.

Tests have demonstrated that the Implant Magnet in combination with the BI300 Implant is MRI conditional for up to 1.5 Tesla. Subjects that receive the Baha Attract System will receive an MRI card, for use by radiologists to evaluate and plan any MRI examination. Subjects that have received radiation therapy at the same side of the skull where the Baha Attract will be positioned are excluded from the investigation.

7.3 Risks associated with participation in the clinical investigation

As with any surgical products, there is a risk that unanticipated Adverse Events may occur. The subjects will be closely monitored in the investigation and instructed to contact the responsible investigator if they experience any untoward effect.

7.4 Risk/benefit assessment

The risks are acceptable when weighed against the benefits of the intended performance of the devices used in the investigation.

8 Statistical consideration

8.1 Statistical Design and Objectives

8.1.1 Primary statistical objectives

To compare the Baha Attract System to unaided hearing, via measurement of the following variables in free-field hearing tests:

- Threshold audiometry: PTA4 (mean of 500, 1000, 2000 and 4000Hz)

8.1.2 Secondary statistical objectives

- To compare the Baha Attract System to unaided hearing, via measurement of the following variables:
 - Thresholds audiometry: 250, 500, 1000, 2000, 3000, 4000, and 6000 Hz
 - Adaptive speech recognition in noise (50% performance)
 - Speech perception in quiet (50dB, 65dB and 80dB SPL)
 - HUI Mark 3
 - APHAB
 - SSQ
- To compare the Baha Attract System to the situation where the same sound processor is worn on a Baha Softband, via measurement of the following variables:
 - Threshold audiometry: PTA4 (mean of 500, 1000, 2000 and 4000Hz)
 - Threshold audiometry: 250, 500, 1000, 2000, 3000, 4000 and 6000 Hz
 - Adaptive speech recognition in noise (50% performance)
 - Speech perception in quiet (50dB, 65dB and 80dB)
- Description of all Adverse Events, device deficiencies, surgical variables, demographics, baseline variables, pain, numbness, soft tissue status, implant loss and questions.
- To investigate if the choice of SP Magnet and magnetic retention force changes over time.

8.2 Sample size calculation

8.2.1 Sample size calculation for the primary efficacy analysis:

In order to achieve 90 % power to detect a clinically significant difference of 10 dB in free-field hearing thresholds between the unaided situation and the Baha Attract System at the 6 months visit with Fisher's non-parametric permutation test for paired observation, two-sided test with significance level 0.05, on the ITT population 20 evaluable subjects are needed assuming a within subject standard deviation (SD) of 13.0 dB. The within subject SD for change in PTA4 has been estimated to 12.3 dB in a previous study within Cochlear comparing unaided hearing with a BP100 sound processor on a

Softband versus unaided hearing². To compensate for a 10% drop out rate in the study 22 subjects should be included in the investigation.

8.2.2 Sample size calculation for the for the secondary analysis

In order to achieve 90 % power to detect a clinically significant change of 1.5 dB in free-field hearing thresholds from Softband to the Baha Attract System at the 6 months visit with Fisher's non-parametric permutation test for paired observation, two-sided test with significance level 0.05, on the ITT population 46 evaluable subjects are needed assuming a within subject SD of 3 dB. The within subject SD for change in PTA4 has been estimated to 2.89 dB in a previous study within Cochlear comparing outcomes with a BP100 sound processor on a Softband versus on an abutment².

8.2.3 Overall sample size considerations

In order to achieve 90% power both for the primary analysis (PTA4, Baha Attract vs. unaided) and the secondary analysis of the primary variable (PTA4, Baha Attract vs. Softband), 46 evaluable subjects are needed. To compensate for a 10% drop out rate in the study 52 subjects will be included in the investigation.

8.3 Analysis sets – populations

The Intention-to-Treat population (ITT) will include all subjects who have received the surgical intervention.

The Per Protocol population (PP) will include subjects that have completed the investigation according to the protocol. Subjects that were incorrectly included or were considered major protocol violators should be removed from the PP population.

The Safety population consists of all surgically treated subjects.

The final definition of the analysis sets (ITT, PP and Safety) will be taken at the clean file meeting before database lock.

8.4 General statistical methodology

Since all included subjects will have measurements of the primary and important secondary efficacy variables for unaided hearing, with the sound processor on a Softband and with the Baha Attract System, all statistical analyses will be paired. All statistical analyses will be non-parametric. In order to choose the most powerful test, the Fisher's non-parametric permutation test for paired observations³ will be used for all paired analyses of continuous variables. The permutation tests use the measured values and not only the ranks in the calculations. For paired analysis of dichotomous and ordered categorical variables the Sign test will be used.

The analyses will be performed in the following priority:

1. Baha Attract System vs. Unaided
2. Baha Attract System vs. the sound processor on a Baha Softband

The main efficacy analysis will be performed on the ITT population and complementary efficacy analyses will be performed on the PP population. The main analysis will be performed after the 6 month visit. A complementary analysis will be performed 18 months after the main analysis (24-month visit). All significance tests will be two-sided and performed at the 5% significance level.

The distribution of continuous variables as well as change in continuous variables will be given as n, mean, SD, SEM, Median, Min and Max and the distribution of dichotomous and categorical variables will be given as number and percentages.

Adverse Events, Device deficiencies, Surgical variables, Demographics Baseline, Questions, Magnetic force and Magnet strength variables will only be analysed descriptively.

8.5 Efficacy analysis

8.5.1 Primary efficacy analysis

Primary efficacy analysis will be determined by analysis of change in free-field threshold audiometry: PTA4 (mean of 500, 1000, 2000 and 4000Hz), from unaided versus Baha Attract System at the 6 months visit for the ITT population, using Fisher's two-sided non-parametric permutation test for paired observations at a significance level of 0.05.

8.5.2 Secondary efficacy analyses

Comparison regarding change from unaided hearing to Baha Attract System will be done according to the general methodology with Fisher's non-parametric permutation test for paired observations for the following variables:

- Threshold audiometry: PTA4 (Mean of 500, 1000, 2000 and 4000 Hz) at 4 weeks, 12 and 24 months
- Threshold audiometry: 250, 500, 1000, 2000, 3000, 4000 and 6000 Hz at 4 weeks, 6, 12 and 24 months
- Adaptive speech recognition in noise (50% performance) at 4 weeks, 6, 12 and 24 months
- Speech in quiet (50dB, 65dB and 80dB) at 4 weeks, 6, 12 and 24 months
- HUI3 at 6 and 24 months
- APHAB at 6 and 24 months
- SSQ at 6 and 24 months

Comparison of the Baha Attract System with the same sound processor worn on a Softband will be done according to the general methodology with Fisher's non-parametric permutation test for paired observations for the following variables:

- Threshold audiometry: PTA4 (Mean of 500, 1000, 2000 and 4000 Hz) at 4 weeks, 6, 12 and 24 months
- Threshold Audiometry: 250, 500, 1000, 2000, 3000, 4000 and 6000 Hz at 4 weeks, 6, 12 and 24 months
- Adaptive speech recognition in noise (50% performance) at 4 weeks, 6, 12 and 24 months
- Speech in quiet (50dB, 65dB and 80dB SPL) at 4 weeks, 6, 12 and 24 months

All secondary efficacy analyses will be two-sided and conducted at the 0.05 significance level.

All secondary efficacy analyses will be performed for both the ITT population and PP population.

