8.10 Statistical Analysis Plan

A statistical analysis plan (SAP) with detailed statistical analyses specified for all variables and time points will be written and signed before the database lock.

9 Administrative Aspects

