4 STATISTICAL METHODOLOGY

4.1 General Methodology

Since all included subjects will have measurements of the primary and important secondary efficacy variables for unaided hearing, with the sound processor on a Softband and with the Baha Attract System, all statistical analyses will be paired. All statistical analyses will be non-parametric. In order to choose the most powerful test, the Fisher's non-parametric permutation test for paired observations will be used for all paired analyses of continuous variables. The permutation tests use the measured values and not only the ranks in the calculations. For paired analysis of dichotomous and ordered categorical variables the Sign test will be used.

The analyses will be performed in the following priority:

1. Baha Attract System vs. Unaided
2. Baha Attract System vs. the sound processor on a Baha Softband

In addition to the change variables the distribution of all efficacy variables will be presented by visit, where applicable.

The main efficacy analysis will be performed on the ITT population and complementary efficacy analyses will be performed on the PP population. The main analysis will be performed after the 6 month visit. A complementary analysis will be performed 18 months after the main analysis (24-month visit). All significance tests will be two-sided and performed at the 5% significance level.

Imputation of missing values will be performed for all efficacy variables. No imputation of baseline values will be made. Imputations will be made according to the following rules:

1. If a value is missing at the end of a patient last observation will be carried forward
2. If a missing value is occurring between two time points with values, an interpolation will be made for continuous variables and for categorical variables the value from the previous visit will be carried forward.

The distribution of continuous variables as well as change in continuous variables will be given as n, mean, SD, SEM, Median, Min and Max and the distribution of dichotomous and categorical variables will be given as number and percentages.

Adverse Events, Device deficiencies, Surgical variables, Demographics Baseline, Questions, Magnetic force and Magnet strength variables will only be analysed descriptively.

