4.10.2 Secondary Efficacy Analyses

Comparison regarding change from unaided hearing to Baha Attract System will be done according to the general methodology with Fisher's non-parametric permutation test for paired observations for the following variables:

- Threshold audiometry: PTA4 (Mean of 500, 1000, 2000 and 4000 Hz) at 4 weeks, 12 and 24 months
- Threshold audiometry: 250, 500, 1000, 2000, 3000, 4000 and 6000 Hz at 4 weeks, 6, 12 and 24 months
- Adaptive speech recognition in noise (50% performance) at 4 weeks, 6, 12 and 24 months
- Speech in quiet (50dB, 65dB and 80dB) at 4 weeks, 6, 12 and 24 months
- HUI3 at 6 and 24 months
- APHAB at 6 and 24 months
- SSQ at 6 and 24 months

Comparison of the Baha Attract System with the same sound processor worn on a Softband will be done according to the general methodology with Fisher's non-parametric permutation test for paired observations for the following variables:

- Threshold audiometry: PTA4 (Mean of 500, 1000, 2000 and 4000 Hz) at 4 weeks, 6, 12 and 24 months
- Threshold Audiometry: 250, 500, 1000, 2000, 3000, 4000 and 6000 Hz at 4 weeks, 6, 12 and 24 months
- Adaptive speech recognition in noise (50% performance) at 4 weeks, 6, 12 and 24 months
- Speech in quiet (50dB, 65dB and 80dB SPL) at 4 weeks, 6, 12 and 24 months

Magnetic force studied both total and by SP magnet. Changes in SP magnet strength will also be presented graphically in a flow graph.

All secondary efficacy analyses will be performed for both the ITT population and PP population. PTA4 will also be analyzed for the PP population in the same fashion as in the primary analysis.

Analyses of Threshold Audiometry, Adaptive speech recognition in noise and Speech in quiet, BC Direct, HUI, APHAB and The Speech, SSQ will be a made totally and also by SSD and Conductive/Mixed patients. This will be made only for the ITT populations.

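### Does the Attract versus Softband comparison, which sets the sample size, need a prespecified confidence interval, a 1.5 dB reading rule and a formal gate?

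*Protocol*

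**What the plan says.** Protocol 8.2.1 needs 20 evaluable subjects for the primary comparison with unaided hearing (10 dB, SD 13.0 dB). Protocol 8.2.2 seeks 90% power to detect "a clinically significant change of 1.5 dB in free-field hearing thresholds from Softband to the Baha Attract System", with an SD of 3 dB. Protocol 8.2.3 then lets that comparison fix the size: for 90% power on both the primary analysis and "the secondary analysis of the primary variable (PTA4, Baha Attract vs. Softband), 46 evaluable subjects are needed", which becomes 52 after allowing for 10% dropout. SAP 1.4 repeats all of this.

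The analysis is a paired Fisher permutation test. SAP 4.10.2 says: "Comparison of the Baha Attract System with the same sound processor worn on a Softband will be done according to the general methodology". Protocol 8.5.2 sets the level: "All secondary efficacy analyses will be two-sided and conducted at the 0.05 significance level". SAP 4.1 fixes the summaries: "The distribution of continuous variables as well as change in continuous variables will be given as n, mean, SD, SEM, Median, Min and Max". No confidence interval is mentioned.

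On ordering, Protocol 8.4 and SAP 4.1 say "The analyses will be performed in the following priority" and list unaided first and Softband second, with no condition attached. Protocol 7.1 gives an expectation: "It is expected that the audiological performance of the Baha Attract System will be similar to, or somewhat better than, Baha on a Softband". Protocol 8.10 promises a SAP with "detailed statistical analyses specified for all variables and time points". The SAP keeps the Protocol's method, and its section 6 reports no changes.

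**The concern.** This comparison more than doubles the evaluable number in a surgical study, yet its only planned inference is a test of zero change. The sponsor expects the devices to be similar or Attract to be somewhat better. A non-significant p-value does not establish similarity, and a significant one does not establish a change of 1.5 dB: at the planned size an observed mean of about 0.89 dB is enough for significance. If nothing says in advance how the estimate is read against 1.5 dB, the choice between similar, better and unclear is made in an open study after the data are known.

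Secondly, the priority list gives an order but no condition. Every secondary test runs at 0.05, and PTA4 is one of 12 Softband tests at 6 months (1 PTA4, 7 frequencies, 1 noise, 3 quiet). That counts the whole ITT population only; the PP repeats and the two hearing-loss subgroups come on top. At stake is the standing of a significant Softband result.

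**Working it through.** **Inputs.** Protocol 8.2.1 to 8.2.3 and SAP 1.4: 10 dB with SD 13.0 dB; 1.5 dB with SD 3 dB (2.89 dB in the earlier Softband versus abutment study); two-sided 0.05; 90% power; 10% dropout. Paired design, so one-sample formulas apply to the change. Normal data are assumed below.

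**The plan's own figures.**
- Primary: noncentral t gives n = 20, power 90.3%. This matches.
- Softband: n = (3 × (1.960 + 1.282) / 1.5)² = 42.03, so 43 by the normal formula. Noncentral t gives 44. At the stated 46, power is 91.3% by t and about 91% by simulation of the sign-flip permutation test.
- Dropout: 46 / 0.9 = 51.1, so 52. This matches.
- At n = 20 the Softband comparison would have 56% power, so it does drive the sample size.

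**The interval available from the planned summaries.** SEM = 3 / √46 = 0.442 dB. Half-width = 2.014 × 0.442 = 0.89 dB. At n = 52: 2.008 × 0.416 = 0.84 dB. Only the reported n, mean and SEM are needed. The t and permutation powers agree closely, so a t interval is a good approximation to inverting the planned test.

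**How often a null would be unclear, if 1.5 dB were read as a two-sided margin on a 95% interval.** At n = 46 a non-significant mean between 1.5 − 0.89 = 0.61 dB and 0.89 dB leaves 1.5 dB inside the interval. Simulated share of all trials that are non-significant with the interval reaching ±1.5 dB (SD 3 dB):

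| True difference | n = 46 | n = 52 |
|---|---|---|
| 0 dB | 13% | 7% |
| 0.5 dB | 21% | 14% |
| 1.0 dB | 21% | 14% |

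The n = 52 column is relevant because ITT is everyone operated on, and SAP 4.1 fills missing post-baseline efficacy values by carrying forward or interpolating; it takes the SD as unchanged by imputation. With a 90% interval (two one-sided 5% tests) the n = 46 figure at a true 0 falls to about 5%.

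**What a reading rule would settle.** An interval that excludes 0 but contains 1.5 dB would be read only as showing a difference, which the planned test already says. At n = 46 this happens in about 59% of trials at a true 1.0 dB and about 89% at a true 1.5 dB, the design alternative.

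**What a gate would do.** Primary power at n = 46 (10 dB, SD 13.0 dB) is 99.9%. Taking the tests as independent, joint power is 0.9992 × 0.9128 = 0.912, against 0.913 without a gate. If both null hypotheses were true and the tests independent, two ungated tests would give 1 − 0.95² = 9.75% family-wise error. When the primary effect is real, the Softband test is at 5% with or without the gate.

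**The case for a change.** The strongest case for a change is that the sponsor itself chose 1.5 dB, powered for it at 90% and enlarged the study for it, so the plan should say how the result will be read. The SAP was meant to hold the detail and only repeats the Protocol. Adding an interval and a sentence costs no subjects. The SD is also borrowed from a Softband versus abutment comparison. If it were 4 dB (an assumption in neither document), the half-width would be 2.014 × 4 / √46 = 1.19 dB, and about 55% of trials would be unclear at a true difference of 0.

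Much of this stands as fact. No interval is named, 1.5 dB never reappears in an analysis section, and the ordering carries no stated condition. The same silence covers the primary's 10 dB.

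What does not follow is that the planned analysis is unsound. The objective is to compare, and the sizing is for detecting a change; the paired test matches both. The expectation of similarity sits under anticipated benefits and is not a hypothesis. Using 1.5 dB as an equivalence margin would be a new choice, and the documents do not make it. The 4 dB case widens the interval, but the reported SEM would show that width to any reader.

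**Conclusion.** No change is needed. Followed as written, the plan gives a valid test of the difference it was sized to detect, together with the estimate and SEM from which the interval follows by one multiplication. The missing interval is a reporting detail that analysts fill sensibly. A ±1.5 dB rule would be a debatable addition that leaves most trials unresolved at true differences of 1.0 to 1.5 dB. The gate would cost and gain practically nothing at 99.9% primary power, with a priority order already stated and the Softband test already identified in Protocol 8.2.2 by comparator, visit, population, test and level.

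The residual ambiguity, if a reader chose to use 1.5 dB as a margin, is about 7% to 13% of trials at a true 0 and 14% to 21% at 0.5 to 1.0 dB. These figures assume normal changes, SD 3 dB, n between 52 and 46, and a 95% interval; a larger SD would raise them. The primary analysis, the sample size and the safety analyses are unaffected.
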